2. To compare type 1 and 3 immunogenicity of one or three doses of bOPV with the same number of doses of bOPV co-administered with nOPV2.
3. To assess the presence of fecal viral shedding (as determined by real-time RT-PCR) over time following one dose of nOPV2, bOPV, or co-administered nOPV2 and bOPV.
4. To estimate household transmission of nOPV2 by assessing the presence of fecal viral shedding (as determined by real-time RT-PCR) among siblings of vaccine recipients.
5. To assess the occurrence and genomic characteristics of intertypic recombinants in stool specimens of vaccine recipients and siblings after one dose of nOPV2 given with or without bOPV.

Methods:

This is an open-label randomized clinical trial. Vaccine recipient participants will be enrolled and randomized at 6 weeks to one of three arms:

- A: nOPV2 @ 6, 10, and 14 weeks
- B: nOPV2 + bOPV @ 6, 10, and 14 weeks
- C: bOPV @ 6, 10, and 14 weeks

For each vaccine recipient, a sibling below 10 years of age will be selected for participation as a sibling.

Outcome measures/variables:

Poliovirus antibody titers to types 1, 2 and 3 will be measured in sera extracted from vaccine recipient blood collected at 6, 10, 14, and 18 weeks. Antibody titers at 6 weeks of age will be the assumed starting point for the expected decline in maternal antibody assuming a half-life of 28 days. Shedding of poliovirus will be measured from stool specimens collected from vaccine recipients and one sibling each at 1, 2, and 4 weeks post-vaccination in Arm A and at 2 and 4 weeks post-vaccination in Arms B and C. Intertypic recombinants will be characterized in a subset of stool specimens collected from vaccine recipients and siblings.

Description of the Research Project

Hypothesis to be tested:

Does this research proposal involve testing of hypothesis: No Yes (describe below)

Primary hypotheses to be tested are:

1. Type 2 immune response after two doses of nOPV2 with bOPV is non-inferior to the immune response observed after two doses of nOPV2 given alone (10% non-inferiority margin).
[Primary objective: 1]
2. Type 1 and 3 immune responses after two doses of bOPV with nOPV2 are non-inferior to the immune responses observed after two doses of bOPV given alone (10% non-inferiority margin).
[Primary objective: 2]

Secondary hypotheses to be tested are:

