If feasible based on guidelines/recommendations related to the COVID-19 pandemic (e.g., physical distancing), the study will also be conducted at the clinical trial unit (CTU), Dhaka. The study area includes the adjoining slum and non-slum areas of icddr,b Mohakahli, Dhaka - Kunipra, Arjat Para, Nakhalpara, Korail, Begunbari, Chairman bari and Badda. Participants will attend CTU, which is about one kilometer from the areas. The population is approximately 300,000 and literacy is ~50%. It is stable with low socio-economic conditions. The population is mainly engaged in industrial labour, garment factory, small businesses and rickshaw pullers.

Study staff will identify infants eligible to be vaccine recipients through house-to-house visits at the two proposed sites of Mirpur and Mohakahli.

Study Design

This is an open-label, non-inferiority, balanced three arm randomized clinical trial assessing immunogenicity of poliovirus vaccines. Vaccine recipients will be identified through active surveillance of new births in the community and parents will be requested to participate through home visits by local field workers. Vaccine recipients will be enrolled at 6 weeks of age, randomly assigned to one of the three arms and followed to 18 weeks of age.

Inclusion Criteria

Criteria for both vaccine recipient and sibling must be met for enrolment in the trial.

Vaccine Recipient

1. Healthy infants 6 weeks of age (range: 42–48 days).
2. Parents that consent for participation in the full length of the study.
3. Parents that can understand and comply with planned study procedures.
4. Infant has at least one sibling aged <10 years living in the same household that is eligible for participation in the study and can be enrolled at the same time as the vaccine recipient.

Sibling

1. Healthy child aged <10 years.
2. Sibling of the vaccine recipient and resides in the same household.
3. Parents that consent for participation in the study until and including the Clinic Visit at 10 weeks (age of vaccine recipient).
4. Parents that can understand and comply with planned study procedures

Exclusion Criteria

If either vaccine recipient or sibling meets the exclusion criteria, then neither can be enrolled in the trial.

Vaccine Recipient

1. Parents, infants, and siblings who are unable to participate in the full length of the study (e.g., plan to move away from the study area during the study period).

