5. One blood specimen (1 ml) will be collected from the vaccine recipient by venipuncture.
6. The first dose of study vaccines will be administered to the vaccine recipient, as directed by study arm.
7. The vaccine recipient will be observed for 30 minutes to monitor for any adverse reactions from the blood collection or administration of study vaccines.
8. The vaccine recipient will receive the recommended routine childhood vaccinations, except polio vaccination. Routine polio vaccines will be replaced by the study vaccine.
9. Clinical information will be collected about the sibling. The sibling must be present at this visit so that he/she may be examined by a medical officer but does not need to be present for any subsequent clinic visits.
10. Schedule the household visit(s) and the next clinic visit.

Phone call or home Visit (24–48 hours after the first study vaccination) [All arms]

1. A study staff will contact the parents of the vaccine recipient to inquire and record any potential adverse events after the first study vaccination.
2. This phone call or visit will be conducted 24–48 hours after the first study vaccination visit.

Home Visit – 7 weeks of age [Arm A only]

Home Visit #1 (two days prior to 7 weeks of age)

1. The study field worker will visit the vaccine recipient's home and provide two plastic screw-cap stool containers to the mother. She will review the stool collection procedures with the mother, including sibling sampling.
2. The study field worker will complete the top portion of the study questionnaire.

Home Visit #2 (7 weeks of age)

1. Mother will collect stool specimens from the vaccine recipient and sibling. If possible, mother will collect fresh stool from each child's diaper or have the child defecate into a clean plastic pot. Mother will be asked to collect stool about the size of one adult thumb (8 grams). She will place the containers with the collected stool specimens immediately into the freezer (if available) or in a cool place in the home. The same procedures will be used for collecting stool specimens from the sibling. Mother will immediately notify the study field worker after each stool collection.

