5. The vaccine recipient will receive the recommended routine childhood vaccinations, except polio vaccination. Routine polio vaccines will be replaced by the study vaccine.
6. Schedule the next visit.

Study Clinic Visit – 14 weeks of age [All arms]

During this visit, the following procedures will be conducted:

1. The medical officer will complete the eCRF and examine the vaccine recipient.
2. One blood specimen (1 ml) will be collected by venipuncture.
3. Study vaccines will be administered, as directed by study arm.
4. The vaccine recipient will be observed for 30 minutes to monitor for any adverse reactions to the study vaccine.
5. The vaccine recipient will receive the recommended routine childhood vaccinations, except polio vaccination. Routine polio vaccines will be replaced by the study vaccine.
6. Schedule the next visit.

Study Clinic Visit – 18 weeks of age [All arms]

During this visit, the following procedures will be conducted:

1. The medical officer will complete the eCRF and examine the vaccine recipient.
2. One blood specimen (1 ml) will be collected by venipuncture.
3. Completion of study activities.
4. Vaccine recipients in Arms A and B will be given the first of three bOPV doses. Note: Arm B will be given three doses of bOPV to account for possible immunologic interference during co-administration of bOPV with nOPV2. All vaccine recipients will be given the first of two fIPV doses.

Timing of Evaluations

Entry/eligibility evaluations

- Entry evaluations will be completed at 6 weeks of age.
- Blood collection and study vaccine administration are planned during the study entry evaluation at 6 weeks of age. Blood will be collected before administration of any study vaccines. On the date of enrolment, study vaccines will be administered only if adequate blood specimen has been collected. If blood cannot be collected on the day of enrolment, study vaccine recipients will be discontinued from the study.
- The window for entry evaluation including collection of blood and administration of vaccine is 42–48 days of age.

Post-entry evaluations and follow-up

- After the first enrolment visit (6 weeks of age, range 42–48 days), the window for study visits is +/- 3 days.
- Blood will be collected before any study or EPI vaccines are administered.
- Stool collection from vaccine recipients and one sibling each will take place at 8 and 10 weeks of age for all Arms, and additionally at 7 weeks for Arm A only.

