Note: For a non-inferiority comparison with a 10% margin, the minimum sample size required for type-2 response of assumed 90% seroconversion is smaller than that for type-1 and type-3 response of assumed 85% seroconversion. As this is a balanced trial, minimum sample size is determined by the larger sample size requirement.

To assess transmissibility of nOPV2 among infants receiving one dose of nOPV2 vaccine and their siblings, two power calculations were computed to: 1) detect at least one transmission event and 2) estimate transmission rate. Both power calculations were based on the established sample size for the primary objectives and expected shedding rate. Shedding rates were estimated using mOPV2 shedding rates from the mOPV2 transmission study in Bangladesh [26] as a comparator and using a simulation model which includes shedding duration and decline in type 2 immunity. All power calculations for the simulation are based on the expected shedding at day 14 post-vaccination. As there are two additional follow-up points and opportunities to observe transmission, the reported power calculations are likely a lower-bound.

Based on the expected recruitment size of 265 vaccine recipients in the nOPV-2 only Arm (Arm A) and 265 next youngest siblings, many of which are expected to be under the age of 5 years, there is evidence of sufficient power to detect transmission events, as well as to estimate a reasonable confidence interval for shedding prevalence. Using sample sizes for the primary objectives, the probability of detecting at least one household transmission event is close to 1. Using our nOPV2 simulation model, we estimate prevalence and 95% CI of shedding to be 53% among vaccine recipients (46.4 – 59.5%) and 23% (17.8 – 28.8%) among siblings under the age of 5 years.

Table 4: Sample size of study arms

Arms		Unadjusted sample size	Enrolment target*
A	nOPV2	238	265
B	nOPV2/bOPV	238	265
C	bOPV	238	265
Total		714	795

* Adjusted for 10% attrition

Outcome variables

Poliovirus antibody titers to types 1, 2 and 3 will be measured in sera extracted from blood collected at 6, 10, 14, and 18 weeks of age. Seropositivity is defined as reciprocal polio neutralizing antibody titers of at least 1:8. Immune response will be defined as either seronegative vaccine recipients (<1:8 titers)

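### Stool visits are set by infant age but labelled by weeks since dose 1, and the protocol never says which date the ±3-day window counts from

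*Protocol*

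**What the plan says.** All references are to the protocol.

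- **Dose 1.** The inclusion criteria admit "Healthy infants 6 weeks of age (range: 42–48 days", and Timing of Evaluations repeats the range for the vaccine: "The window for entry evaluation including collection of blood and administration of vaccine is 42–48 days of age".
- **Stool schedule.** The operative instructions use the infant's age. Timing of Evaluations says "Stool collection from vaccine recipients and one sibling each will take place at 8 and 10 weeks of age for all Arms", with a further 7-week stool in Arm A. Study Procedures has "Home Visit #2 (7 weeks of age" for that collection and "Home Visit #1 (two days prior to 7 weeks of age" for the kit delivery. Table 1, Table 3 and the household visit forms also go by age.
- **Labels.** The Project Summary describes the same specimens as collected "at 1, 2, and 4 weeks post-vaccination in Arm A and at 2 and 4 weeks post-vaccination in Arms B and C". The outcome variables and the general analytical section define shedding and household transmission by those intervals. Table 5 equates 10 weeks of age with 4 weeks after vaccination.
- **Planning.** For household transmission, "All power calculations for the simulation are based on the expected shedding at day 14 post-vaccination".
- **Tolerance.** The only general rule is "After the first enrolment visit (6 weeks of age, range 42–48 days), the window for study visits is +/- 3 days". The per-protocol stool restriction allows 3 days either side of the scheduled visit date. Neither rule names its starting date.

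**The concern.** Age and time since vaccination coincide only for an infant dosed on day 42. For any later dose an exact age-based stool date arrives early by the number of days the dose was late, up to six. A six-day error matters most for the 7-week stool, where the intended interval is only seven days.

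The results most exposed are absolute rates at a named time: the Arm A one-week shedding estimate, the first-dose time course, and household transmission. Transmission is descriptive and has no Sabin 2 comparison group. A sibling stool taken a day or two after the infant's dose has had little opportunity to show spread from that infant, yet it could count as a one-week observation. The per-protocol population would not necessarily remove it: if the scheduled date is age-based, such a stool is fully compliant.

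**Working it through.** **Inputs.** Dose 1 on day 42 to 48 of age (inclusion criteria; Timing of Evaluations). Stool visits at 7, 8 and 10 weeks, or days 49, 56 and 70 if read as exact ages (Study Procedures). Kit delivery two days before each. Tolerance ±3 days.

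**Formula.** Days since dose 1 = 7 × (visit age in weeks) − (age in days at dose 1).

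**Step 1: reproduce the stated intervals.** With dose 1 on day 42: 49 − 42 = 7, 56 − 42 = 14, 70 − 42 = 28. These are the stated 1, 2 and 4 weeks.

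**Step 2: apply the permitted enrolment range under each reading.**

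| Stool | Exact age, nominal | Exact age, with ±3 days | Completed weeks | Counted from dose 1, ±3 days |
|---|---|---|---|---|
| 7 weeks (Arm A) | 1–7 | −2 to 10 | 1–13 | 4–10 |
| 8 weeks | 8–14 | 5–17 | 8–20 | 11–17 |
| 10 weeks | 22–28 | 19–31 | 22–34 | 25–31 |

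For exact ages the nominal limits are 49 − 48 to 49 − 42, 56 − 48 to 56 − 42, and 70 − 48 to 70 − 42. The third column widens each limit by 3 days; its negative values are arithmetic only (see the objection). For completed weeks, the reading that the protocol itself gives to 6 weeks (days 42–48), the limits are 49 − 48 to 55 − 42, 56 − 48 to 62 − 42, and 70 − 48 to 76 − 42.

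**Step 3: average shift.** Assume enrolment is even over the seven days, so that the mean dose day is 45. On exact ages the mean intervals are 49 − 45 = 4, 56 − 45 = 11 and 70 − 45 = 25 days, each 3 days short of its label. Dose days 46, 47 and 48 (3 of 7, or 43%) put the nominal one-week stool at 3, 2 and 1 days after the dose. Dose days 42 to 45 (4 of 7) keep all nominal stools within 3 days of days 7, 14 and 28.

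On completed weeks there is spread but no average shift. The mid-points are days 45, 52, 59 and 73, so the stools lie 52 − 45 = 7, 59 − 45 = 14 and 73 − 45 = 28 days after the dose, give or take 6.

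**Step 4: kit delivery.** On exact ages the first Arm A kit is due on day 49 − 2 = 47. For an infant dosed on day 48 that is one day before the dose, so the instruction cannot be followed as written.

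**The case against.** The strongest reply is that the age anchor is inferred. The protocol never states a visit as day 49, 56 or 70, and several places suggest counting from the dose. The visits are booked at the enrolment visit, after the vaccine is given. The endpoints are in weeks since vaccination. Later bloods are described as 4 weeks after vaccine administration, siblings are followed for 4 weeks and infants for 12. If staff count from dose 1, the intervals are right. This stands as evidence of likely intent. It does not remove the contradiction, because no passage sets a stool date from the dose, although the protocol does anchor to the dose where it chooses: the safety contact is timed in hours after the first vaccination. With two sites planned, each could follow a different calendar.

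Four stronger readings might be inferred, and the documents do not support them.

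- **A stool or kit before the dose.** The negative limit in the table is not a realistic event. The 7-week visit is for Arm A only, and the arm is revealed only at randomization.
- **A proven systematic shift of 3 days.** That needs both exact-day ages and even enrolment. Under completed weeks only the spread remains.
- **Damage to the main conclusions.** The primary objectives use serology, not stool. Randomization should balance stool timing where arms are compared on the same specimens. Transmission counts a positive at any of the timepoints, so an early first stool does not discard the later ones.
- **Wrong planning prevalences (53% in infants, 23% in siblings under 5).** No shedding curve is given, so neither the size nor the direction of any discrepancy can be computed.

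Visit and stool dates are already recorded, so analysis by actual interval is possible and may be left to a statistical analysis plan that is not shown. That would label the stools correctly, but it cannot supply a day-7 or day-14 specimen that was collected on another day.

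**Conclusion.** The point holds as an unresolved contradiction between the visit schedule and the outcome definitions, with an unnamed anchor for both the visit window and the per-protocol window. Followed as exact ages, the protocol permits a one-week stool one day after dose 1 and an 8-week stool 8 days after it. Followed as completed weeks, a one-week stool may lie anywhere from 1 to 13 days after the dose. Only dose anchoring delivers what the labels and the day-14 planning basis claim. The ranges rest on the document's own figures; the means and the 43% also rest on assumed even enrolment.

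The consequence is confined to secondary objectives 3–5. It is greatest for the Arm A 7-week stool and for absolute shedding and household transmission rates, and least for the 10-week stool. Severity is moderate.

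**What to change.** - State that the 7-week (Arm A) and 8-week (all arms) stool visits are scheduled 7 and 14 days after the date of the first study vaccination, ±3 days, with kits still delivered two days ahead (days 5 and 12).
- Apply the per-protocol stool window to those dates.
- Report every stool, including the one tied to the 10-week visit, by actual days since dose 1, using the dates already on the forms.
- Reconcile the age-based and post-vaccination passages, including Table 5. No change to vaccine timing is proposed.

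The cost is a short amendment, a changed visit-date calculation in REDCap and some analysis wording. There are no added visits or samples. It should be settled before enrolment, because a specimen missed at the intended interval cannot be recovered.

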who become seropositive ($\geq 1:8$) (seroconversion) or vaccine recipients who demonstrate at least a four-fold increase in titer (boosting). Baseline maternal antibody titer will be determined at 6 weeks of age and the estimated maternal antibody level at each blood collection will be calculated assuming an exponential decline with a half-life of 28 days. Vaccine recipients and siblings will be categorized for shedding poliovirus through results from multiple real-time PCR (rRT-PCR) assay designed to detect poliovirus. Household transmission will be defined as present if siblings test positive for nOPV2 vaccine virus at either 1, 2, or 4 weeks following the vaccine recipient's vaccination at 6 weeks of age. nOPV2 vaccine virus in stool specimens from vaccine recipients and siblings will be further characterized through high-resolution Illumina RNA sequencing. Intertypic vaccine-derived recombinants will be characterized in stool collected from study vaccine recipients and siblings.

Randomization

Vaccine recipients will be randomized to one of three arms using a block randomization scheme. The randomization algorithm will be generated by CDC staff and executed in REDCap. The randomization algorithm will not be known to study staff in icddr,b. Randomization assignment will be revealed after completing enrolment procedures, when study staff "click" on randomization button on the study tablets. Therefore, study staff enrolling and managing vaccine recipients will not have *a priori* knowledge of randomization scheme. As this is an open-label trial, the arm assignment of vaccine recipients will be known to study staff and the vaccine recipient's parents after randomization. Laboratory staff processing blood samples in Bangladesh will not have *a priori* knowledge of randomization scheme but will know the arm assignment after randomization. However, CDC laboratory staff testing for poliovirus antibody titers will remain blinded throughout the study.

Timeline of activities

Activities	Year 1 (months)					
	2	4	6	8	10	12
Protocol development/IRB approval, Staff training/site preparation						
Enrolment						
Start and completion of vaccination						
Follow up of vaccine recipients						
Lab testing						
Dissemination/Publications						

Data Analysis

General Issues

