This is an open-label, non-inferiority, randomized clinical trial that will compare immune response to types 1, 2 and 3 polioviruses of nOPV2 and bOPV when co-administered compared to nOPV2 and bOPV given alone. The study will recruit 795 vaccine recipients in three arms. Vaccine recipients will be enrolled at 6 weeks of age and followed until 18 weeks of age, for 12 weeks of follow-up. For each vaccine recipient enrolled, one sibling will be enrolled at the same time and followed for 4 weeks .

General Analytical Issues

The data will be analysed by study investigators that include epidemiologists and statisticians. Statistical packages that will be used for the analysis include R, SAS and STATA.

For assessing immunity to polio, seropositivity is defined as reciprocal polio neutralizing antibody titers

of at least 1:8. Immune response will be defined as either seronegative vaccine recipients ($<1:8$ titers) who become seropositive ($\geq 1:8$) [seroconversion] or vaccine recipients who demonstrate a four-fold

increase in titer (boosting). Baseline maternal antibody titers will be determined at 6 weeks of age and the estimated maternal antibody level at each blood collection will be calculated assuming an exponential decline with a half-life of 28 days.

For assessing fecal viral shedding, detection of nOPV2 or bOPV vaccine virus in stool specimens from vaccine recipient or sibling at either 1, 2, or 4 weeks post-vaccination of the vaccine recipient at 6 weeks of age will be defined as positive for viral shedding. For assessing the detection of household transmission, presence of transmission will be defined as the sibling of the vaccine recipient testing positive for nOPV2 vaccine virus at either 1, 2, or 4 weeks post-vaccination of the vaccine recipient at 6 weeks of age.

To characterize the intertypic recombinants in a subset of stool specimens of vaccine recipients and siblings after one dose of nOPV2 given with or without bOPV, amplicon sequences from long-read sequencing methods will be used to confirm genome structure. Amplicon sequences will also be mapped against all three Sabin vaccine reference sequences to generate coverage plots.

Primary Analytical Approach

The primary analytical approach will be intention-to-treat. To evaluate the primary objectives, the intention-to-treat analysis will be restricted to vaccine recipients who:

- Have not withdrawn consent for receipt of vaccines and follow-up evaluations since enrolment.

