- Vaccine recipient received the scheduled study vaccination at 6 weeks of age.

Table 5: Study arms comparison, study endpoints, and results by objective

Study Objective	Study Arms Comparison	Endpoint (vaccine recipient age)	Results Included in Analysis
Primary			
1. To compare type 2 immunogenicity of two doses of nOPV2 with two doses of nOPV2 co-administered with bOPV.	A vs. B	14 weeks	Serology: 6, 10, 14 weeks
2. To compare type 1 and 3 immunogenicity of two doses of bOPV with two doses of bOPV co-administered with nOPV2.	C vs. B	14 weeks	Serology: 6, 10, 14 weeks
Secondary			
1. To compare type 2 immunogenicity of one or three doses of nOPV2 with the same number of doses of nOPV2 co-administered with bOPV.	A vs. B	10 weeks	Serology: 6, 10 weeks
		18 weeks	Serology: 6, 10, 14, 18 weeks
2. To compare type 1 and 3 immunogenicity of one or three doses of bOPV with the same number of doses of bOPV co-administered with nOPV2.	C vs. B	10 weeks	Serology: 6, 10 weeks
		18 weeks	Serology: 6, 10, 14, 18 weeks
3. To assess the presence of fecal viral shedding (as determined by real-time RT-PCR) over time following one dose of nOPV2, bOPV, or co-administered nOPV2 and bOPV.	Descriptive with comparisons of A vs. B and B vs. C	10 weeks (i.e. 4 weeks post-vaccination)	Stool: 7 (Arm A only), 8, 10 weeks from vaccine recipient
4. To estimate household transmission of nOPV2 by assessing the presence of fecal viral shedding (as determined by real-time RT-PCR) among siblings of vaccine recipients.	Descriptive	10 weeks (i.e. 4 weeks post-vaccination)	Stool: 7 (Arm A only), 8, 10 weeks from sibling
5. To assess the occurrence and genomic characteristics of intertypic recombinants in stool specimens of vaccine recipients and siblings after one dose of nOPV2 given with or without bOPV.	Descriptive with comparison of A vs. B	10 weeks (i.e. 4 weeks post-vaccination)	Stool: 8, 10 weeks from vaccine recipient and sibling

Adverse Events (AEs)

Safety will be assessed by:

- Incidence rate of solicited systemic AEs 24–48 hours after the first study vaccination.
- Incidence rate of unsolicited AEs during entire study period.
- Incidence rate of serious AEs during entire study period.

Data Safety Monitoring Plan (DSMP)

Records to be kept

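### The any-visit shedding definition counts a week-1 stool that only Arm A provides, so the combined A vs B recipient shedding rate is inflated in Arm A

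*Protocol*

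**What the plan says.** - **Definition.** Data Analysis, General Analytical Issues, gives one shedding status for all arms: "detection of nOPV2 or bOPV vaccine virus in stool specimens from vaccine recipient or sibling at either 1, 2, or 4 weeks post-vaccination" counts as positive. It makes no exception for an arm that lacks one of these visits.
- **Schedule.** The Project Summary places stool collection "at 1, 2, and 4 weeks post-vaccination in Arm A and at 2 and 4 weeks post-vaccination in Arms B and C". Post-entry evaluations and follow-up says the same by age: "at 8 and 10 weeks of age for all Arms, and additionally at 7 weeks for Arm A only". Tables 1 and 3 agree.
- **Comparison.** Table 5 describes secondary objective 3 as "Descriptive with comparisons of A vs. B and B vs. C", and its column of included results reads "Stool: 7 (Arm A only), 8, 10 weeks from vaccine recipient".
- **Contrast within the same table.** For secondary objective 5, which also compares A with B, the included results are "Stool: 8, 10 weeks from vaccine recipient and sibling", the visits that both arms share.
- **Siblings.** Under Outcome variables, "Household transmission will be defined as present if siblings test positive for nOPV2 vaccine virus at either 1, 2, or 4 weeks" after the recipient's first dose. Table 5 marks the corresponding objective 4 as descriptive and names no pair of arms.

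**The concern.** A status that is positive if any sample is positive depends on how many samples are taken. Here the number differs between the two arms being compared. The Protocol accepts this principle in its Sample size section, where it calls its day-14 power calculations a likely lower bound because further follow-up points give more opportunities to observe transmission.

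The sampling error has a fixed direction: an extra sample can only raise Arm A's rate. A higher rate in the nOPV2-only arm would be read as bOPV reducing type 2 shedding. If there were real interference, its size would be overstated; if there were none, the table could still suggest it. The Protocol says that the trial's data are meant to inform outbreak-response decisions, and the Justification for this Study names inhibition between the two vaccines (there for immunogenicity) as a question of particular interest.

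**Working it through.** **Inputs**
- Samples per recipient after the first dose: three in Arm A (weeks 1, 2, 4), two in Arm B (weeks 2, 4), from the schedule sections and Table 5.
- Expected nOPV2 shedding in recipients: 53% (95% CI 46.4–59.5%), at day 14, from Sample size.
- Recipients per arm: 238 before the attrition allowance, 265 enrolled, from Table 4.
- q, the share of children negative at both week 2 and week 4 who were positive at week 1: not in the Protocol. I assume 0.05 to 0.30.

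**The plan's own figures first.** 238 / 0.90 = 264.4, rounded up to 265, as stated. An exact binomial interval for 126/238 (53%) is 46.4–59.4%, against the stated 46.4–59.5%, so the stated precision is about that of 238 children. The 53% itself is simulation output and cannot be rebuilt.

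**Formula.** Let p be the probability of being positive at week 2 or week 4, the same in both arms (no true effect of co-administration on shedding).
- Arm B: P(positive) = p
- Arm A: P(positive) = p + (1 − p)q
- Artefact, A minus B: (1 − p)q

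**Numbers.** The 53% refers to day 14 alone, so it is a floor for p. A larger p leaves a smaller remainder and a smaller artefact, so p = 0.70 is shown as well (assumed).

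| q (assumed) | Arm A, p = 0.53 | Artefact | Arm A, p = 0.70 | Artefact |
|---|---|---|---|---|
| 0.05 | 0.53 + 0.47 × 0.05 = 0.554 | 2.4 points | 0.715 | 1.5 points |
| 0.10 | 0.577 | 4.7 points | 0.730 | 3.0 points |
| 0.20 | 0.624 | 9.4 points | 0.760 | 6.0 points |
| 0.30 | 0.671 | 14.1 points | 0.790 | 9.0 points |

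The Protocol states no test for this comparison. Purely as a scale: if a two-sided 5% test of two proportions were applied at 238 per arm with p = 0.53, the chance of a nominally significant result with Arm A higher would be about 7%, 18%, 55% and 88% for the four values of q, against 2.5% with no artefact.

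**On shared visits.** With positivity defined on weeks 2 and 4 only, both arms have probability p and the expected difference is p − p = 0. The same holds at week 2 alone or week 4 alone. Arms B and C follow the same schedule, so unequal sampling does not touch B vs C.

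**The case against.** **The objective is secondary and descriptive, and sits under the exploratory questions.** True, and it limits the consequence: the primary non-inferiority comparisons use serology and are untouched. But Table 5 plans named comparisons between arms, and a descriptive difference can mislead as well as a tested one.

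**Objective 3 concerns shedding over time, and Table 5 gives its endpoint as 10 weeks, a visit all arms share.** Visit-specific comparisons would indeed be unbiased. However, the only definition of shedding-positive in the Data Analysis section is cumulative, and the neighbouring column of Table 5 brings in the Arm A-only stool. The Protocol does not say which governs.

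**A statistical analysis plan could settle this.** It could, but the point is not something left open. The Protocol states the definition, the comparison and the included samples, and together they give unequal ascertainment. Objective 5 shows that the restriction to shared visits was available.

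Four stronger readings are tempting and are not supported:
- *That the sibling results are a biased A vs B comparison too.* The sibling definition has the same unequal sampling, but no arm comparison is planned for objective 4, and objective 5, which does compare A with B and includes siblings, uses the shared visits.
- *That Arm B children count as positive on any of three serotypes, against one in Arm A.* The phrase covering either vaccine's virus is loose enough to allow this. But the section on specimen testing describes type-specific PCR, and the pairings A vs B and B vs C match the type-specific logic of the immunogenicity objectives. Pooling is one possible reading, not a stated rule.
- *That a real effect could not be separated from the artefact.* It could: 8- and 10-week stools are collected in every arm.
- *That the artefact has a known, large size because week 1 is near peak shedding.* The Protocol gives no week-1 shedding figure and no q.

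**Conclusion.** The point holds for one combined endpoint in one secondary, descriptive comparison: any-visit recipient shedding, A vs B. As written, Arm A's rate is inflated relative to Arm B's by (1 − p)q under equal true shedding. With p = 0.53 and q assumed between 0.05 and 0.30, this is about 2 to 14 points; with p = 0.70 it is about 2 to 9 points. The sign of the sampling artefact follows from the design; its size rests on the assumed q and on using a day-14 figure for p. No data are lost, and the conclusions on immunogenicity stand. This should be corrected before the shedding analysis, but it does not threaten the trial's main results.

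**What to change.** In General Analytical Issues and in the Table 5 row for secondary objective 3:
- Define recipient shedding for the A vs B comparison on the 8- and 10-week stools only, as Table 5 already does for objective 5. Visit-specific rates at those two ages can be shown beside the combined rate.
- State the serotype: type 2 for A vs B, types 1 and 3 for B vs C. This removes the ambiguity about pooling and needs no extra testing, because the PCR is already type-specific.
- Report the 7-week stool as a separate descriptive result for Arm A.
- If Arm A and Arm B sibling transmission rates are ever shown side by side, base both on the same two visits and keep the three-visit rate as an Arm A result.

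The cost is a wording change. No visit, sample or assay is added, and the week-1 stool leaves only the between-arm figure.
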